4. INVESTIGATIONAL PLAN

4.1. Study Drugs

The investigational drugs in this study include INCB050465 and INCB039110. All study subjects will receive these study drugs in an open-label manner, as oral, self-administered agents. INCB050465 will be administered in all parts of the study. INCB039110 will only be administered in Part 2 and Part 3 Expansion Cohorts E.

4.2. Overall Study Design

The study consists of 4 parts. The overall study design is shown in [Figure 2](#). Monotherapy dose escalation (Part 1) will determine recommended dose(s) to be explored further. The recommended dose(s) will be defined as dose(s) at least equivalent to the PAD (a dose that produced substantial pharmacologic target inhibition) and no higher than the MTD.

[figure not shown]
Part 2 will evaluate the combination of INCB050465 and INCB039110 to determine the recommended dose(s) of the combination.

Expansion (Part 3), which consists of 5 cohorts, will evaluate the recommended dose(s) of INCB050465 as monotherapy and in combination with INCB039110. The monotherapy dose-expansion cohorts will evaluate INCB050465 in subjects with B-cell malignancies, indolent lymphoma, DLBCL, and HL. Note that expansion cohorts for INCB050465 monotherapy may explore more than 1 recommended dose and schedule to obtain long-term safety data on multiple dose levels and schedules. The combination expansion cohorts will evaluate the chosen combination dose of INCB050465 and INCB039110 in subjects with B-cell malignancies.

Part 6 will include a safety assessment of INCB050465 in combination with the chemotherapy regimen R-ICE (rituximab, ifosfamide, carboplatin, and etoposide) in subjects with B-cell malignancies, followed by an expansion cohort in DLBCL. Timing for the initiation of Part 6 will be determined by the sponsor based on emerging data from Parts 1 and 3 of the study. Note, for purposes of consistency and database completion, this will remain Part 6.

Note: With Amendment 10, Protocol-required procedures have been reduced for ongoing subjects.

Figure 2: Study Design

4.2.1. Part 1 – Monotherapy Dose Escalation of INCB050465

Dose escalation will be conducted with a 3 + 3 design, with the exception that the first cohort (dose level of 5 mg QD) will be a single subject cohort. There will be an observation period of 21 days before enrollment of the next cohort and administration of the next dose level. Subjects who receive at least 17 days of INCB050465 at the level assigned to that cohort will be considered evaluable for determining tolerability of dose. Subjects enrolling but not meeting these criteria may be replaced in order to fill the cohort.

- The initial cohort will consist of a single subject (the cohort may include an additional subject to ensure completion of 1 evaluable subject through Day 21); the initial dose will be 5 mg QD.
 - If a Grade 2 or greater AE is observed, the cohort will be expanded to 3 subjects. If the initial cohort is expanded to 3 subjects, the safety assessment will follow the 3 + 3 design. Subsequent cohorts will have increases in the dose of INCB050465 limited to no more than 50%.
 - If a Grade 2 or greater AE is not observed, the dose of INCB050465 will be increased to 10 mg QD (or 5 mg BID depending on PK data) in the subsequent cohort, and dose escalation will be conducted using a 3 + 3 dose titration design. After the 10 mg QD (or 5 mg BID) dose level cohort, subsequent increases in the dose of INCB050465 will be limited to no more than 50%.
 - If the MTD has been exceeded or the PAD has been achieved in the initial cohort, this cohort may be expanded to at least 3 subjects and a lower dose of INCB050465 (eg, 2.5 mg QD) may be explored.

- With the 3 + 3 design, each cohort will enroll a minimum of 3 subjects. If no DLTs are observed in the initial 3 subjects, the next cohort will begin enrollment. If 1 DLT is observed in the first 3 subjects, 3 additional subjects will be enrolled in the cohort. If DLTs occur in > 1 of the first 3 subjects or the total cohort of 6 subjects, then the MTD will be deemed to have been exceeded and the next lower tolerable dose level will be deemed to be the MTD.
- If the dose increment has been 100% and deemed exceeding the MTD, an intermediate dose level may be explored (eg, from 10 mg QD to 7.5 mg QD).
- Dose increases will occur using 1 of 2 options: 1) increasing the number of tablets taken at each QD administration, or 2) increasing the dose frequency to BID. For example, based on safety in a cohort receiving 5 mg QD, the total daily dose might be increased 2-fold in the next cohort by using a 5 mg BID regimen or by using a 10 mg QD regimen, depending on emerging PK data. The dose regimen will be designed to maintain a suitable peak-to-trough ratio and minimize accumulation.

If a dose level is reached that provides a suitable profile of pharmacologic target inhibition (PAD) before reaching the MTD, then this dose may be deemed a recommended dose(s) and used to move to Part 3 monotherapy dose expansion, as well as taken to Part 2 for testing in the combination. Dose escalation of the monotherapy may continue at doses above the PAD until the MTD is reached or dose escalation is stopped. In the event that the half-life suggests alternative schedules will provide optimum target inhibition, additional cohorts may be evaluated (eg, BID administration).

4.2.2. Part 2 – Dose Escalation With the Combination of INCB0504065 and INCB039110

Dose escalation will proceed using a 3 + 3 design with a starting dose of INCB050465 approximately 25% (rounded down to the nearest tablet size combination) below the recommended dose determined in Part 1 followed by escalation of INCB050465 in combination with INCB039110 300 mg QD. Escalation of the dose of INCB050465 will continue in combination with INCB039110 300 mg QD until the recommended dose is determined. If the starting dose of INCB050465 cannot be combined safely with INCB039110 300 mg QD, INCB039110 at 200 mg QD will be tested. If that combination is tolerated, escalation of INCB050465 will proceed with INCB039110 200 mg QD. Additional dose de-escalation may occur with INCB050465 if DLTs occur with a causality that can be reasonably assigned to INCB050465. Additional dose escalation or de-escalation of INCB039110 and/or INCB050465 may be considered if supported by emerging safety, PK, [REDACTED] data in this combination.

4.2.3. Part 3 – Expansion

Monotherapy Expansion Cohorts A, B, C, and D will open when the recommended dose(s) is chosen from Part 1, independently from Part 2. Recommended dose(s) will be at least equivalent to the PAD and no higher than the MTD (or the highest dose tested). Expansion Cohort A will enroll subjects with B-cell malignancies, Cohort B will enroll subjects with HL, Cohort C will enroll subjects with DLBCL, and Cohort D will enroll subjects with indolent lymphoma. Note that expansion cohorts for INCB050465 monotherapy may explore more than 1 recommended dose and schedule to obtain long-term safety data on multiple dose levels and schedules.

When the recommended dose for Phase 2 combination therapy has been determined from Part 2, enrollment will proceed simultaneously for Expansion Cohort E, which will enroll subjects with B-cell malignancies. Details regarding the dose expansion cohorts are described in [Table 1](#).

If ≥ 5 subjects in the first 15 subjects of any cohort, cumulatively, (or more than 33% of subjects in cohorts larger than 15 subjects) experience DLTs during Cycle 1, then further enrollment to the cohort will be stopped, and a lower dose level may be explored. Based on emerging data, the sponsor may decide on the number of subjects with a specific subtype of an indication to be enrolled into each expansion cohort (eg, non-GCB or GCB in DLBCL) or specific tumor types to be enrolled in Cohorts A and E (eg, mantle cell lymphoma).

Table 1: Part 3 Expansion Cohorts

Part	Cohort	Population	# of Subjects	Treatment
3	A	B-cell malignancies	15-30	INCB050465 monotherapy
	B	HL	≤ 15	
	C	DLBCL ^a	≤ 15	
	D	Indolent lymphoma	≤ 30	
	E	B-cell malignancies	≤ 15	INCB050465 + INCB039110

^a Based on emerging data, the sponsor may decide on the number of subjects with a specific subtype of an indication to be enrolled (eg, non-GCB or GCB).

4.2.4. Part 6 – Dose Evaluation and Expansion With the Combination of INCB050465 and R-ICE

Initiation of Part 6 dose evaluation will be dependent on preliminary data from Parts 1 and 3 of the study. Dose evaluation would proceed in subjects with DLBCL using a 3 + 3 design with a starting dose of INCB050465 approximately 25% (rounded down to the nearest tablet size combination) below the recommended dose determined in Part 1 in combination with the chemotherapy components at the following doses in a 21-day cycle for a total of 3 cycles:

- Rituximab 375 mg/m² given on Day 1 and Day 2 of Cycle 1, and on Day 1 of Cycles 2 and 3.
- Ifosfamide 5000 mg/m² continuous IV infusion over 24 hours on Day 3.
 - Mesna should be added to ifosfamide infusion.
- Carboplatin AUC = 5 mg/mL (maximum dose 800 mg) IV infusion on Day 3.
- Etoposide 100 mg/m² IV on Days 3 to 5.

Note: As an alternative to the Protocol-specified dose and schedule, R-ICE may be administered according to institutional practice with medical monitor approval.

If tolerated, the dose of INCB050465 will be escalated to the recommended dose in combination with R-ICE. INCB050465 will be given daily or intermittently and may be continued until a criterion is met for treatment discontinuation. If the starting dose of INCB050465 cannot be combined safely with R-ICE at the schedule described above, the dose of INCB050465 will be reduced to 25% below the dose first administered in combination with R-ICE. Additional dose de-escalation may occur with INCB050465 if DLTs occur with a causality that can be reasonably

assigned to INCB050465. Additional dose de-escalation of INCB050465 and intermittent schedules may be considered if supported by emerging safety, PK, [REDACTED] data in this combination. Following the identification of a tolerable dose of the combination of INCB050465 and R-ICE (a dose less than or equal to the MTD), expanded Cohort L will be opened to further evaluate the safety, efficacy, PK, [REDACTED] as described in [Table 2](#).

Table 2: Part 6 Expansion Cohort

Part	Cohort	Population	# of Subjects	Treatment
6	L	DLBCL ^a	~15	INCB050465 + R-ICE

^a Based on emerging data, the sponsor may decide on the number of subjects with a specific subtype of an indication to be enrolled (eg, non-GCB or GCB).

If ≥ 5 subjects in Cohort L experience DLTs during Cycle 1, further enrollment to the cohort will be stopped, and a lower dose level may be explored.

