1.2.4. Clinical Summary of INCB050465

As of 02 SEP 2016, data were available for 46 subjects who received INCB050465 administered orally at QD doses of 5 mg (n = 1), 10 mg (n = 3), 15 mg (n = 3), 20 mg (n = 15), 30 mg (n = 20), and 45 mg (n = 4). The median duration of treatment was 104 days. Adverse events observed in $\geq 20\%$ of subjects were nausea, diarrhea, vomiting, neutropenia, fatigue, hypokalemia, and fever. No \geq Grade 3 treatment-related AEs were reported in $\geq 10\%$ of subjects. Serious AEs (SAEs) that occurred in ≥ 2 subjects included colitis (n = 3), diarrhea (n = 3), and pyrexia, pneumonia, dehydration, exfoliative dermatitis, and hypotension (n = 2 each). Eleven of the 46 subjects (24%) discontinued study treatment due to the following AEs: colitis, diarrhea, pneumonitis, rash, exfoliative dermatitis, psoriasis, neutropenia, pneumonia, and hypercalcemia. All but 1 of these events occurred after the 9-week disease assessment. No liver function test abnormalities > Grade 1 were reported while subjects were receiving study treatment. No dose-limiting toxicities were identified, and the maximum tolerated dose was not reached.

As of 02 SEP 2016, 20 objective responses as reported by investigators were observed at doses ≥ 10 mg QD in 41 evaluable subjects. Objective responses were observed in 5 subjects with DLBCL (n = 14), 6 subjects with follicular lymphoma (n = 6), 4 subjects with marginal zone lymphoma (n = 4); 3 subjects with mantle cell lymphoma (n = 4), 1 subject with Hodgkin lymphoma (n = 8), and 1 subject with CLL (n = 5). The objective response rate in evaluable subjects with NHL (n = 28) was 64%. Among the 18 objective responses observed in subjects with NHL, 17 (94%) were observed by the time of the first disease assessment.

Pharmacokinetics analysis showed the T_{max} is 0.5 to 1 hour, the terminal half-life is approximately 8 to 12 hours, and exposure appeared to be dose-proportional between 5 mg QD and 45 mg QD at steady state. The pharmacodynamic analyses demonstrated robust and sustained pathway inhibition at all dose levels tested. Refer to the [INCB050465 IB](#) for further details.

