9.2. Selection of Sample Size

The total sample size estimate is up to approximately 150 subjects in this study. Approximately 20 subjects will be enrolled in Part 1 monotherapy dose escalation, and approximately 12 subjects will be enrolled in Part 2 combination dose escalation. Expansion Cohort A will enroll between 15 and 30 subjects, and Cohorts B, C, D, and E will enroll up to 15 subjects each.

In Part 6, up to 12 subjects will be enrolled in the safety evaluation followed by an expansion cohort of up to 15 subjects. The exact number of subjects treated will depend on the number of subjects required per dose level and the number of dose levels studied. During the 3 + 3 dose escalation in Part 1 and Part 2, the probabilities of dose escalation from that dose level for various DLT rates are given in [Table 13](#).

Table 13: Probability of Dose Escalation for Specific Dose-Limiting Toxicity Rates During 3 + 3 Dose Escalation

True DLT Rate	Probability of Dose Escalation
10%	90.6%
20%	70.9%
30%	49.4%
40%	30.9%
50%	17.2%
60%	8.2%

Note that if escalation occurs at the highest dose level during the study, then the MTD is at or above the last dose level. If the study stops at the first dose, then the MTD is below the first dose level. In either of these cases, the prescribed doses may need to be altered in order to determine the MTD.

In the expansion cohorts the evaluation of 15 subjects, each will provide a $\geq 90\%$ chance of identifying a toxicity with a true event rate of 15%.

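### In monotherapy expansion Cohorts A to D the DLT stopping rule is counted per disease cohort, although a cohort may hold several doses, so DLTs at a more toxic dose can be diluted by a safer one

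*Protocol*

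**What the plan says.** The rule in Protocol Section 4.2.3 is that if at least 5 "subjects in the first 15 subjects of any cohort, cumulatively" ("or more than 33% of subjects in cohorts larger than 15 subjects") have Cycle 1 DLTs, "then further enrollment to the cohort will be stopped, and a lower dose level may be explored". The synopsis repeats it.

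Table 1 and the text above it define cohorts by disease: "Expansion Cohort A will enroll subjects with B-cell malignancies, Cohort B will enroll subjects with HL", Cohort C takes DLBCL and Cohort D indolent lymphoma. The same section notes that "expansion cohorts for INCB050465 monotherapy may explore more than 1 recommended dose and schedule". Neither place says that DLTs are counted by dose.

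The SAP, written for Protocol Amendment 3, summarises safety by dose group (Section 5.2). It contains no expansion stopping rule, and it lists DLTs only for Parts 1 and 2 (Section 8.2.2).

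**The concern.** The unit of counting is the disease cohort, but the quantity being monitored belongs to a dose. If two doses share a cohort, DLTs at the more toxic dose are divided by a denominator that includes subjects who never received it. The stated consequence, exploring a lower dose level, makes sense only if the cohort holds one dose. The multi-dose sentence and the stopping rule therefore do not fit together.

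Safety and dose selection form the primary objective, and there is no Data Monitoring Committee (Section 8.7). Pooling can let a dose above one-third toxicity go on enrolling. It can also halt an acceptable dose because of the other one.

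**Working it through.** **Inputs from the protocol.** The limits are 5 of the first 15, then more than 33% (Section 4.2.3). In a full cohort of 30 that means 10 DLTs, since 9/30 = 30% and 10/30 = 33.3%. On size, "Expansion Cohort A will enroll between 15 and 30 subjects" (Section 9.2), which agrees with Table 1. Cohort D is up to 30 in Table 1 but up to 15 in Section 9.2, so the 30-subject example rests on Cohort A. The documents give no DLT rates by dose and no dose splits; those below are assumptions.

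**The plan's own figure.** Section 9.2 claims at least a 90% chance of seeing a toxicity with a true rate of 15% in 15 subjects: 1 − 0.85^15 = 0.913, which reproduces. That is the chance of at least one event. No operating characteristic is given for the stopping rule.

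**One dose in the cohort.** P(Bin(15, p) ≥ 5) is 48.5%, 78.3%, 94.1% and 99.1% at p = 30%, 40%, 50% and 60%. At 45% it is 88.0%.

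**Cohort of 30: 15 subjects at 10%, 15 at 45%.** This is the like-for-like case, because 15 subjects receive the toxic dose under either way of counting.
- Final look only: P(Bin(15, 0.10) + Bin(15, 0.45) ≥ 10) = 28.4%. This leaves out the first-15 check.
- Checked after each subject (stop at 5 up to subject 15, then at 6 for 16-18, 7 for 19-21, 8 for 22-24, 9 for 25-27, 10 for 28-30), doses alternating: 49% if the safer dose goes first, 54% if the toxic dose goes first.
- At least 5 of 15 in the 45% dose alone: 88.0%.

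Order of enrolment matters. With the toxic dose at 40%, the pooled rule stops with probability 42.1% under alternating enrolment (toxic dose first) and 21.6% if all of the safer dose is enrolled first, against 78.3% counted alone. If all 15 at the toxic dose enrol first, the first-15 check is already a per-dose count and nothing is diluted.

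**Cohort of 15: 8 subjects at 10%, 7 at 40%.** Pooled, P(Bin(8, 0.10) + Bin(7, 0.40) ≥ 5) = 27.1%. Applying the one-third fraction to the 7 (3 is the first count above one-third): P(Bin(7, 0.40) ≥ 3) = 58.0%.

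**Range for a cohort of 15 with 8 at the toxic dose and 7 at the safer dose:**

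| Toxic-dose DLT rate | Pooled, safer dose 5% | Pooled, safer dose 10% | ≥ 3 of 8 within toxic dose |
|---|---|---|---|
| 30% | 11.1% | 17.5% | 44.8% |
| 40% | 25.7% | 34.2% | 68.5% |
| 50% | 45.6% | 54.2% | 85.5% |
| 60% | 67.0% | 73.5% | 95.0% |

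If the other dose has no DLTs, 4 of 8 subjects (50%) at one dose can have a DLT without a stop.

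**Moving the count of 5 unchanged to a small dose group.** P(Bin(8, 0.40) ≥ 5) = 17.4%, below the pooled 34.2%. This would make detection worse.

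**Cost of a per-dose check.** As an example, take one look at subject 7 (stop at 3 or more) plus at least 5 of 15. The chance of stopping is 3% at a true 10% rate and 23% at 20%. For at least 5 of 15 alone it is 1% and 16%.

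**The case against.** The strongest reply is that the assumed rates look remote.
- Section 1.2.4 reports 15 subjects at 20 mg and 20 at 30 mg, no DLTs identified, and the MTD not reached. If that covers all subjects rather than escalation only, one-sided 95% upper bounds are 1 − 0.05^(1/20) = 14% at 30 mg and 1 − 0.05^(1/15) = 18% at 20 mg.
- Expansion doses may not exceed the MTD or the highest dose tested, and by Table 13 a dose with a 40% DLT rate passes a 3 + 3 level only 30.9% of the time.
- Section 5.5.1 considers all safety data, Section 8.7 provides continuous sponsor monitoring, and Section 4.6 has a study-level one-third criterion.
- Under Amendment 10 the current schedules (Tables 9 and 10) are for ongoing subjects, so the rule may have little enrolment left to act on.
- Sections 5.5.1 and 9.4.1 speak of dose cohorts and treatment cohorts, which might suggest a per-dose reading.

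Most of this stands as a limit on urgency. It does not repair the rule. None of these safeguards sets a per-dose limit in expansion. The dose-cohort wording concerns escalation decisions and data summaries, while Table 1 fixes the Part 3 cohorts by disease.

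A reader might infer from the 15 and 20 subjects that dilution is already happening. Those numbers exceed the 3 to 6 that a 3 + 3 level holds, so expansion very probably used both doses. The dose-normalised Cohort A food-effect results (also Section 1.2.4) hint at mixing. Neither shows both doses within one cohort, and no DLTs were reported to dilute.

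**Conclusion.** The point holds as a defect in how the rule is specified. In Cohorts A to D it pools doses whenever a cohort holds more than one, and under the assumed 10% and 45% rates, with 15 subjects each and alternating enrolment, that lowers the chance of stopping from 88% to about 49-54%. In the 15-subject example the fall is from 58% to 27%.

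The size rests on assumed rates, splits and enrolment order; it measures the rule and does not predict toxicity in this trial. Three limits apply. The multi-dose sentence does not cover Cohort E or Cohort L. Regimens with the same Cycle 1 dosing, such as daily dosing throughout and daily dosing that becomes weekly after 9 weeks (Section 1.7.1), are not diluted by pooling. Sponsor judgement could still stop a dose, so enrolment may continue, not must.

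It would be tempting to set the 27% against the 78.3% for 15 subjects all at 40%. That compares 7 exposed subjects with 15, so part of the gap is sample size; 58% is the fair comparator.

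**What to change.** Reconcile the stopping rule with the multi-dose sentence in Section 4.2.3 and the synopsis.
- Keep the cohort-level rule.
- Where a cohort holds regimens that differ in Cycle 1 dosing, add a separate DLT count for each such dose against the protocol's existing one-third fraction.
- Do not carry over the absolute count of 5 to a dose with fewer than 15 subjects.
- Do not split by schedule where Cycle 1 dosing is identical; that shrinks denominators and gains nothing.
- The sponsor should choose the minimum number of subjects before the per-dose count applies, and report the operating characteristics of the combined rule. The 3-of-7 and 3-of-8 figures above are illustrations of the one-third fraction, not proposed limits.

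The cost is a short protocol change, with no extra subjects or data, and some added chance of halting an acceptable dose. That chance depends on the minimum chosen. If Part 3 enrolment is closed, the sponsor should say so, since the change would then have little practical effect.

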4.2.5. Crossover to Combination Therapy After Monotherapy Treatment

For subjects who discontinue INCB050465 monotherapy for a reason described in Section 5.7.1, the investigator may feel that the best option for the subject is to enroll in a combination therapy offered in this Protocol. Prior use of a PI3K inhibitor is not prohibited per the inclusion/exclusion criteria for combination cohorts. Therefore, subjects who discontinue INCB050465 may be allowed to cross over to combination therapy. In these cases, the subject must meet the eligibility criteria for the cohort they will cross over to, and the sponsor must approve the crossover.

